1. AMENDMENT HISTORY

Amendment No.	Protocol Version No.	Date issued	Author(s) of changes	Details of Changes made

2. SYNOPSIS

Study Title	Feasibility study investigating the P revention of post-operative gastro-oesophageal anastomotic L eaks with the U se of a surgical adhesive, Bio G lue – the PLUG trial: a single-arm trial			
Internal ref. no.	PHT/2019/72			
Problem statement	A leak from the gastro-oesophageal anastomosis in the post-operative period following an oesophagectomy is a serious, and unfortunately not uncommon, complication (1) (2). Leaks are known to prolong stay, worsen long term outcomes and have significant morbidity as well as mortality and need for return to theatre (3) (4). For patients suitable for resection in the form of oesophagectomy, current evidence shows that minimally invasive oesophagectomy, with a laparoscopic and thoracoscopic approach, gives better outcomes (5) (6).			
	This study will use a pre-existing surgical adhesive in a novel way, to supplement standard gastro-oesophageal anastomotic techniques with BioGlue, with the aim of assessing technical feasibility of using the product in this operation, monitoring for additional complications, and observing rates of anastomotic leak. BioGlue is a mix of purified bovine serum albumin (BSA) and glutaraldehyde which are mixed at the time of application, within the applicator tip. BioGlue reaches full strength within two minutes. The BioGlue has been used widely, particularly in cardio- thoracic and vascular surgery and has been in circulation since 1998 (7). It is licensed for use in the alimentary system but, as yet, there has not been documented use in oesophagogastric anastomoses The study will be conducted at a single centre, and include patients undergoing an elective oesophagectomy for cancer.			
Research question / hypothesis	Is it technically feasible to use BioGlue as an additional measure to supplement standard procedure in the creation of a gastro-oesophageal anastomosis in the context of a minimally invasive oesophagectomy? Are there any additional complications observed as a result of using BioGlue? What is the observed anastomotic leak rate in patients receiving BioGlue?			
Study Design	Single-arm trial. Patients undergoing minimally invasive oesophagectomy for treatment of cancer will have BioGlue applied to the oesophago-gastric anastomosis in addition to the standard anastomotic technique.			
Study Participants	Inclusion Criteria: 1. aged 18 years and above			

	 2. planned for elective minimally invasive oesophagectomy at Queen Alexandra Hospital 3. Able to provide informed consent Exclusion criteria: Provious adverse reaction to PieClue or one of ite 				
	constituent ingredients.				
Planned Sample Size	30				
Follow-up duration	6 weeks post-surgery				
Planned Study Period	1 year				
Primary Objective	To assess whether it is technically feasible to use BioGlue at the anastomosis for oesophagectomy				
Secondary Objectives	To describe adverse events up to 6 weeks post-surgery.				
Objectives	To describe surgical process indicators and surgical outcomes.				
Primary Endpoint	Technical feasibility of applying the BioGlue				
Secondary Endpoints	Post-operative complications up to six weeks, graded with the Clavien- Dindo scale Anastomotic leak rate All-cause mortality up to 6 weeks follow up Operative duration Time to discharge from hospital Unplanned return to ITU Unplanned return to theatre Unplanned return to surgical high care unit Acceptability of the product to the surgeons and the theatre team (assessed using qualitative methods) Number of CT scans Use of antibiotics (duration, indication and type)				
Intervention (s)	Application of adhesive BioGlue in addition to standard anastomotic formation in patients undergoing minimally invasive oesophagectomy.				

3.	ABBREVIATIONS
AE	Adverse event
BSA	Bovine serum albumin
CPET	Cardiopulmonary exercise testing
СТ	Computed tomography
ITU	Intensive treatment unit
MDT	Multi-disciplinary team
MIO	Minimally invasive oesophagectomy
NHS	National Health Service
PPI	Public patient involvement
PRA	Patient research ambassador
QAH	Queen Alexandra Hospital, Portsmouth Hospitals NHS Trust
RCT	Randomised controlled trial
SAE	Serious adverse event
TMG	Trial management group
TOG	Trials oversight group

4. BACKGROUND AND RATIONALE

1. Oesophagectomy is the surgical treatment of oesophageal malignancy

The incidence of adenocarcinoma of the oesophagus has been observed to be rapidly increasing in the UK and the western world although incidence of squamous cell carcinoma of the oesophagus has been steadily declining. Cancer of the oesophagus (all types) is the sixth most common cancer in men and the ninth most common cancer in women worldwide with an observed six-fold increased incidence in men (8). The management of carcinoma of the oesophagus remains challenging (9). If a patient presents with malignancy which can be treated with curative intent, the surgical option is oesophagectomy. This was traditionally performed as an open operation but has progressed over the last 25 years and is now quite widely offered as a minimally invasive procedure – with laparoscopic and thoracoscopic stages (10). Within QA all oesophagectomies are undertaken with the aim of completion using minimally invasive techniques.

2. Anastomotic leaks are a major cause of perioperative morbidity and have a significant financial impact

One of the major risks of oesophagectomy is of a leak from the gastro-oesophageal anastomosis. Leak rates from the gastro-oesophageal anastomosis are quoted by NICE as 20%, which correlates with similar international figures e.g. The Dutch National database (1) (11). An anastomotic leak leads to prolonged in-hospital stay, can require an unplanned return to theatre, return to ITU and is associated with mortality as well as morbidity (2). Increases in mortality ranging from 18.2-35% have been quoted in the literature (12). As well as the distress, pain and other negative outcomes for the patients, the need for re-operation, return to ITU and increased length of stay come at significant financial cost. A Dutch team showed that a minor complication increases the cost of surgery for oesophageal cancer from an average of €59,167. Specifically, they showed the average cost of a patient who had suffered an anastomotic leak to be €44,268 (€20,792 higher than when the patient suffer no complications) (13).

3. BioGlue is already used, licensed and has been shown to be safe

BioGlue is a mix of purified bovine serum albumin (BSA) and glutaraldehyde which are mixed at the time of application, within the applicator tip. BioGlue has been used since 1998 with its main applications in cardiothoracic and vascular surgery. Despite its regular safe use, there are risks associated with its application which (as described in the product literature) include: inflammatory and immune response, allergic reaction, mineralization of tissue, local tissue necrosis, luminal obstruction, thrombosis and thromboembolism, pulmonary emboli, injury to normal tissue, and possible transmission of infectious agents from material of animal origin. [name] within QA had used BioGlue uneventfully in bariatric surgery (14) (15) (16) (17).

4. There is no documented use of this material in the context of preventing anastomotic leaks following oesophagectomy

There is no evidence of an existing completed or uncompleted study which is investigating the use of this material in the way this study proposes. There have been some small studies looking into the use of certain surgical adhesives in the context of preventing anastomotic leaks and a systematic review of these showed overall beneficial outcomes in the intervention groups, but not of this type of adhesive (11). There is a single arm prospective study in recruitment stage investigating the use of Porcine Fibrin Sealant (Bioseal®) to reinforce gastro-oesophageal anastomoses in patients undergoing oesophagectomy [Study of Porcine Fibrin Sealant in Preventing Cervical Anastomotic Leakage for Esophageal or Junctional Carcinoma. (PLACE020). Yang Hong, Sun Yat-sen University. NCT03529266]. Our trial of a different material will add valuable information in the attempt to reduce the incidence of post-operative anastomotic leaks following oesophagectomy.

5. Why use this product in this way now?

As outlined, the risk of anastomotic leak is high and is associated with high levels of morbidity and mortality. There have been a very large number of studies attempting to find the best surgical technique for creation of the gastro-oesophageal anastomosis to prevent leaks. Although a number of different techniques have been shown to be safe, there are few which have shown a significant benefit to changes in surgical technique (18) (19). There are numerous surgeons around the world attempting to reduce the risk of this major operation and this is a novel approach to an ongoing complex challenge.

6. AIMS AND OBJECTIVES

This study aims to investigate if the use of BioGlue, in addition to standard technique, is technically feasible and safe to provide evidence to allow for a larger randomised controlled study with the aim of investigating the effect on anastomotic leaks.

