6.2 Secondary Objectives

- 1. To describe adverse events up to 6 weeks post-surgery
- 2. To quantify the leak rate
- 3. To describe surgical process indicators and surgical outcomes

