7. STUDY DESIGN

7.1 Summary of Study Design

This is a feasibility study to investigate the use of BioGlue (a mix of purified bovine serum albumin (BSA) and glutaraldehyde) to reinforce the anastomosis created during a minimally invasive oesophaegectomy. The study will be undertaken at a single centre and consecutive patients will be included up to a total of 30. Patients will receive the standard follow up following oesophagectomy, with a telephone consultation one week after discharge and then clinic appointments at two- and six-weeks. For the purposes of the study, all participants will also be reviewed by the study team six-weeks after the day of surgery. Patients will then continue to be followed up as normal, but outside of the bounds of this study.

The results from this study can guide the researchers in the further use of this product in the wider context of a randomised controlled trial.

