10.3 Randomisation

In this feasibility study the patients will not be randomised. The intervention will be applied to all patients who consent.

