10.6 Definition of End of Study

The end of the study is 6 weeks post-operatively following the last patient's operation.

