CryoLife provide reference to evidence in the literature of these events in experimental animal and human studies investigating its use on cardiac or pulmonary tissue. They do not provide any reference to its use or effects on the alimentary tract (7). Literature review as part of the protocol development has found a number of studies assessing its use and safety on the alimentary tract, none of which have reported these complications. Systematic review of the use of tissue adhesives in gastro-oesophageal anastomosis identified a number of studies in animals and humans (11). None of the above complications were reported; however, it must be noted that the only outcomes measured were collagen synthesis, bursting pressure and anastomotic leak. An RCT comparing the application of BioGlue to reinforce the staple line in stapled haemorrhoidopexy vs standard procedure, found it reduced post-operative complications. Participants who received BioGlue did not have any anastomotic leak, thrombosis, haemorrhage or anal stenosis; all of which occurred in the standard treatment group, and are potential complications detailed in manufactures instructions for use (17). A systematic review of tissue adhesives in gastro-intestinal anastomosis found a range of evidence from animal and human clinical studies, on a number of tissue adhesive products. BioGlue was investigated in 3 of the 48 studies. The review identified no local complications from any of the tissue adhesives, such as tissue damage, luminal stenosis/blockage, injury to nerves, blood vessels, heart or lung parenchyma, or intra-abdominal solid organs (20). All of these review articles highlight the variability between studies and poor overall quality of evidence. Nonetheless the potential complications discussed in the manufacturer's literature have not been found to be significant in any of these studies and provides reassurance that BioGlue is highly likely to be safe in this application.

Participants in the study are at risk of these reactions, however they are so uncommon we believe that with such a small study group it is unlikely to cause any of them harm. The manufacturers instruction for use provides warnings for use of BioGlue in certain situations to avoid these reactions:

- Could contact or obstruct circulating blood flow.
- Could obstruct circulating air or luminal fluid flow.
- Contact with nerves, eyes or unintended tissue.

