14.5 Interim analysis and criteria for early study termination

As this is a feasibility study assessing the ease and safety of application of the glue, there will be no planned interim analysis. Due to the small number of patients needed for the study, and the acceptable leak rate of 20%, it is entirely possible that consecutive participants suffer an anastomotic leak through chance alone. Each anastomotic leak will be reviewed as a serious adverse event. If there are any concerns that a leak has been caused by the BioGlue applied (for example, the anastomosis has become abnormally adherent to structures in the chest at re-operation) then a serious adverse device effect has occurred, and the study paused while this is reviewed. If there are 5 consecutive anastomotic leaks in a row, this will trigger an internal review and an independent data monitoring committee formed and convened to review the study. If there are more SAEs than expected, raised by the research team inputting data, this will be highlighted to the PI. Early termination of the study can then be considered by the PI.

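### Section 6 aims to find out whether BioGlue is safe, but an uncontrolled study of 30 with no safety threshold can only describe adverse events and reveal common device harms

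*Protocol*

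**What the plan says.** Section 6 sets the overall aim: to investigate whether BioGlue, added to standard technique, "is technically feasible and safe to provide evidence to allow for a larger randomised controlled study". The numbered objectives are narrower. Section 6.1 covers technical feasibility only, and the first item of section 6.2 is "To describe adverse events up to 6 weeks post-surgery".

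On design, section 7.1 says that "consecutive patients will be included up to a total of 30", and section 10.3 that "In this feasibility study the patients will not be randomised". Section 10.6 fixes the horizon: "The end of the study is 6 weeks post-operatively following the last patient's operation".

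On the reactions listed by the manufacturer, section 12.1 accepts that participants are at risk but adds that "they are so uncommon we believe that with such a small study group it is unlikely to cause any of them harm". It gives no rate.

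Section 14.2 plans a proportion and its standard error for every yes/no outcome. Section 14.5 opens its explanation of why there is no interim analysis with "As this is a feasibility study assessing the ease and safety of application of the glue". It refers to serious adverse events exceeding what is expected, without a number for what is expected. Section 19 says the results will inform whether a multicentre randomised trial is needed and how it is designed.

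**The concern.** The aim asks a question with a yes-or-no answer (is it safe?) and ties the answer to a later randomised trial. The rest of the protocol supplies nothing from which to answer yes: no comparator, no acceptable device-harm rate and no decision rule. Section 12.1 also expects the listed reactions to be rare enough that probably none will affect this group. If that is right, zero device reactions is the result to expect, and seeing it adds little to what was believed beforehand.

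What is at stake is the weight a zero count can carry when the randomised trial is planned. Section 4 reports no documented use of this adhesive to prevent leaks after oesophagectomy, and section 5 reports no preliminary studies by the investigators. These 30 patients would therefore be the only direct safety evidence at this site that the protocol identifies. The aim should not promise more than they can give, and the planned summary should show how much uncertainty is left.

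**Working it through.** **Inputs.** n = 30 (section 7.1), single arm (section 10.3). The protocol states no device-harm rate, power, precision target or derivation of 30, so there is no planned figure to reproduce. The true risk p of a serious device effect within six weeks is an assumption, taken over 1% to 10%. Patients are treated as independent with the same risk, and all 30 as treated and followed to six weeks.

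**Step 1: chance of a clean result.** P(0 events) = (1 − p)^30.

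| Assumed true risk | P(no event in 30) | P(at least one) |
|---|---|---|
| 1% | 0.99^30 = 74% | 26% |
| 2% | 0.98^30 = 55% | 45% |
| 3% | 0.97^30 = 40% | 60% |
| 5% | 0.95^30 = 21% | 79% |
| 10% | 0.90^30 = 4% | 96% |

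The chance is exactly one half at p = 1 − 0.5^(1/30) = 2.3%. Below that a clean result is more likely than not; above it, it is not.

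**Step 2: what 0 of 30 leaves open.**
- One-sided 95% upper limit: 1 − 0.05^(1/30) = 9.5%.
- Two-sided exact 95% upper limit: 1 − 0.025^(1/30) = 11.6%.

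**Step 3: sample size for a 95% chance of seeing at least one event.** n = ln(0.05)/ln(1 − p), rounded up: 299 at 1%, 149 at 2%, 59 at 5%. This shows scale only; it is not a proposal to enlarge the study.

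**Step 4: what the planned summary would show.** The standard error of a proportion is √[p̂(1 − p̂)/n]. At 0 of 30 it is √(0 × 1/30) = 0. The measure fixed in section 14.2 would thus indicate no uncertainty in exactly the case where the exact upper limit is 9.5% or 11.6%.

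**Step 5: common events.** Section 14.5 refers to an "acceptable leak rate of 20" per cent, which is 0.20 × 30 = 6 leaks expected. P(no leak in 30) = 0.80^30 = 0.1%, so leaks will almost certainly be seen. Without a control arm they are hard to interpret: six or fewer leaks has probability 61% at a true rate of 20%, 35% at 25% and 16% at 30%.

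**The case against.** The strongest reply is that the operative text is already modest. Section 6 is an introductory sentence about investigating, the primary objective is feasibility alone, and section 6.2 only describes. No hypothesis, threshold or success rule exists that a clean result could meet. This stands, and it limits the point to the wording of the aim and the display of zero counts. It also shows that the aim goes further than the objectives beneath it.

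A second reply is that safety here is wider than rare device reactions. Leaks, graded complications, deaths and unplanned returns are all recorded, and many are common. Difficulties with application are recorded and the application is filmed. This also stands: the overall safety record will not be empty. But section 12.1 classes the established complications, leak included, as ones patients face with or without the glue. With no comparator, a modest excess cannot readily be attributed to it.

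Third, the sentence in section 12.1 reassures about participant risk and is not a statement about what the design can detect. That is fair. The conclusion does not depend on it, because the binomial figures hold over the whole assumed range.

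Three stronger readings are tempting and are not supported:
- A reader might infer that a clean result is likely however harmful the glue is. The figures say otherwise: 21% at a 5% risk and 4% at 10%.
- A reader might infer that section 14.5 passes a safety verdict to the randomised trial. It mentions no such trial and speaks of safety of application while explaining the lack of an interim analysis. Only section 6 makes the link.
- A reader might infer that zero events will be published as proof of safety. The protocol does not say so; it says that outcomes will be described and will inform later work.

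**Conclusion.** The point holds in a limited form. The aim in section 6 claims more than a single-arm study of 30 without a safety threshold can deliver. Such a study would usually reveal a device harm of 5% or more (at least one event with probability 79% at 5%, 96% at 10%), but it would more likely than not miss one below about 2.3%. If none is seen, risks up to about 10–12% remain compatible with the data.

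These figures rest on an assumed range of risks, because the protocol states none, and on all 30 patients being treated and followed; fewer would widen the limits. They concern effects arising within six weeks. The primary objective, the sample size and the conduct of the study are unaffected. The one analytical defect is a standard error that falls to zero at zero events. The statistical analysis plan was not available, so this rests on what the protocol itself fixes in section 14.2.

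**What to change.** 1. Reword the aim in section 6 to: technically feasible, and to describe adverse events and device effects up to 6 weeks. This agrees with section 6.2. The link to a later randomised trial can stay.
2. Add to section 14.2 that device effects, and any other binary outcome with a zero count, are reported with an exact 95% confidence limit, because the standard error is zero there.
3. Add to section 14.2 that absence of device effects will be reported as not excluding risks up to about 10–12%, and not as demonstrating safety.

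The cost is a wording amendment and one exact interval per outcome, with no extra patients, visits or data. The downside for the sponsor is a less favourable stated safety claim.

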6.1 Primary Objective

To assess whether the use of BioGlue in addition to standard anastomotic technique is technically feasible in the context of the reinforcement of an oesophago-gastric anastomosis following oesophagectomy.

6.2 Secondary Objectives

- 1. To describe adverse events up to 6 weeks post-surgery
- 2. To quantify the leak rate
- 3. To describe surgical process indicators and surgical outcomes

7. STUDY DESIGN

7.1 Summary of Study Design

This is a feasibility study to investigate the use of BioGlue (a mix of purified bovine serum albumin (BSA) and glutaraldehyde) to reinforce the anastomosis created during a minimally invasive oesophaegectomy. The study will be undertaken at a single centre and consecutive patients will be included up to a total of 30. Patients will receive the standard follow up following oesophagectomy, with a telephone consultation one week after discharge and then clinic appointments at two- and six-weeks. For the purposes of the study, all participants will also be reviewed by the study team six-weeks after the day of surgery. Patients will then continue to be followed up as normal, but outside of the bounds of this study.

The results from this study can guide the researchers in the further use of this product in the wider context of a randomised controlled trial.

7.2 Primary and Secondary Endpoints/Outcome Measures

Primary endpoints:

The technical feasibility of applying the BioGlue.

Secondary endpoints:

- 1. Post-operative complications up to six weeks, graded with the Clavien-Dindo scale
- 2. Anastomotic leak rate
- 3. All-cause mortality up to 6 weeks follow up
- 4. Operative duration
- 5. Time to discharge from hospital
- 6. Unplanned return to ITU
- 7. Unplanned return to theatre
- 8. Unplanned return to surgical high care unit
- 9. Acceptability of the product to the surgeons and the theatre team (assessed using qualitative methods)
- 10. Number of CT scans
- 11. Use of antibiotics (duration, indication and type)

